4.5.4 Analyses of Patient-Reported Outcomes

The [Redacted text block]

4.5.5 Sensitivity Analyses

No sensitivity analyses are planned.

4.5.6 Subgroup Analyses

Subgroup analyses will be conducted for selected endpoints. The following subgroups will be based on:

- [Redacted list item]

[REDACTED]

- | [REDACTED]
- | [REDACTED]
- | [REDACTED]

[REDACTED]

- | [REDACTED]
- | [REDACTED]
- [REDACTED]
- | [REDACTED]
- | [REDACTED]
- | [REDACTED]

[REDACTED]

- | [REDACTED]
- | [REDACTED]

[REDACTED]

- | [REDACTED]
- | [REDACTED]
- | [REDACTED]

[REDACTED]

- | [REDACTED]
- | [REDACTED]

4.6 PHARMACOKINETIC AND PHARMACODYNAMIC ANALYSES

No pharmacokinetic or pharmacodynamic analyses are planned for this study.

4.7 SAFETY ANALYSES

The primary objective for this study is to investigate safety and tolerability of adding nintedanib to treatment with pirfenidone. Consequently, safety endpoints related to patient disposition, early discontinuations and adverse events are of main interest.

Analyses will be descriptive. No confirmatory analyses are defined and no comparative statistics will be generated.

Patients' safety will be assessed further through analyses of treatment exposure, laboratory tests, vital signs, and ECGs.

4.7.1 Treatment Completion/Early Discontinuation

A summary of the number and proportion of patients who complete 24 weeks of combination treatment (with 95% CI) will be presented. A patient is considered to have completed 24 weeks of combination treatment, if the eCRF question "Did the subject complete the treatment?" is ticked "Yes" (eCRF form "Study Drug Completion/Early Discontinuation"). It is expected that these patients have completed the Week 24 visit within expected time window (see Section 4.9).

The number and proportion of patients who complete 24 weeks of combination treatment (with 95% confidence interval (CI)) on pirfenidone at a dose of 1602-2403 mg/d and nintedanib at a dose of 200-300 mg/d will be presented. Average daily dose information as defined in Section 4.7.2 will be used to assess whether a patient completed 24 weeks on target dose.

The number and percentage of patients who discontinued combination treatment because of an adverse event (with 95% CI) will also be presented. This summary comprises patients who have reported "Adverse Event" as the main reason for treatment discontinuation.

The duration of combination treatment will be summarized descriptively. Duration of combination treatment will be defined as the time (days) from combination treatment start date (see Section 4.2.2) to the date subject completed or early discontinued from combination treatment period as per eCRF (Study Drug Completion/Early discontinuation form).

Kaplan-Meier (KM) plots for time to treatment discontinuation will be provided, based on the date subject completed or early discontinued from combination treatment period, as per eCRF (see Section 4.2.5).

Details on treatment and study discontinuations will be listed.

Logistic regression analysis will be used to assess the influence of baseline covariates on the discontinuation rate in an exploratory manner. The following parameters will be used to explain early treatment discontinuation:

- Age (years) at baseline,
- Sex (female = 0, male = 1),
- FVC % predicted at baseline,
- DLco % predicted at baseline.
- Region (US vs non-US)

Further parameters will be analyzed on an exploratory basis.

The regression coefficients for each covariate, together with the standard error and p-value will be presented. Further, odds ratios and 95% confidence intervals will also be given. In addition, a model including all covariates will be investigated in order to assess the consistency of the results.

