4.2.5 Treatment Start and Stop Dates

As this is a combination treatment study, different assessments with respect to study treatment are possible: Pirfenidone alone, nintedanib alone, and combination treatment. To account for this, the following definitions will be made:

Table 4 Definition of Treatment/Combination Treatment Start and Stop Dates

	Treatment start date	Treatment end date
Combination treatment	Date of first administration of nintedanib and pirfenidone on or after the Baseline visit = Start date of combination treatment	Date subject completed or early discontinued from combination treatment period as per eCRF (eCRF form Study Drug Completion/Early discontinuation). = Date of completion or discontinuation from combination treatment
Pirfenidone	Start date of combination treatment	Date of last administration of pirfenidone as recorded in the study drug log for pirfenidone, until the date of completion or discontinuation from combination treatment.
Nintedanib	Start date of combination treatment	Date of last administration of nintedanib as recorded in the study drug log for nintedanib, until the date of completion or discontinuation from combination treatment.

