4.7.2 Exposure of Study Medication

Summaries of dosing, treatment duration, dose interruptions or reductions will be provided for each treatment separately, as well as for combination treatment, if applicable.

Generally, treatments administered from combination treatment start date up to the 'Date subject completed or early discontinued from combination treatment period' as per eCRF 'Study drug completion/Early Discontinuation' will be considered for exposure analyses. All drug records before or after these dates reported in the drug-log will be disregarded. The below definitions are to be interpreted within this time window.

The overall **treatment duration** (weeks), including and excluding dose interruptions, will be summarized descriptively. Also the days with dose interruptions will be given in this presentation.

The overall treatment duration **including** dose interruptions will be defined as follows:

- Overall duration of combination treatment including dose interruptions = [(Date of discontinuation/completion of combination treatment – date of initiation of combination treatment) + 1]/7.

The date of first administration of nintedanib and pirfenidone on or after the Baseline visit will be considered as initiation date of combination treatment (see Section 4.2.1).

- Overall treatment duration of pirfenidone or nintedanib alone including dose interruptions = [(Date of last non-zero dose of treatment received until

**Pirfenidone and nintedanib — F. Hoffmann-La Roche Ltd
Statistical Analysis Plan MA29895, Version 2.0, final, 17 May 2017**

discontinuation/completion of combination treatment – date of initiation of combination treatment) + 1]/7.

The overall treatment duration **excluding** dose interruptions will be derived from the treatment administration panels, considering only days on treatment. When calculating duration of combination treatment, only days where both, pirfenidone and nintedanib, were interrupted will be excluded.

Dose interruptions will be calculated by summing all days where dose (pirfenidone or nintedanib) was interrupted. Combination treatment will only be considered to be interrupted if both, pirfenidone and nintedanib, were interrupted.

The total number of patient days on treatment, including and excluding dose interruptions, and the total number of patient days with dose interruptions, will be presented.

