The **total dose** (mg), the **last dose administered** (mg/d) and the **average daily dose** for each of the study treatments will be presented descriptively. The average daily dose will be calculated by summing up the number of capsules taken during the combination treatment period, divided by the number of days on combination treatment including treatment interruptions, as defined above. Further, frequencies for categories of average daily doses (e.g. <1602, 1602 – 2403, >2403 mg/d for pirfenidone, and <200, 200 – 300, >300 for nintedanib, as well as combinations of both) will be presented.

Dose modifications and dose interruptions will be analyzed for any dose modification or dose interruption, as well as for dose modifications and drug interruptions separately. Numbers and proportions of patients with at least one dose modification or dose interruption will be presented for each treatment separately. Numbers and proportions of patients with 1, 2, 3 or more dose modifications or drug interruptions will be given.

Numbers and frequencies of reasons for dose modification or dose interruption will be presented.

Analyses will be based on the information on dose modifications or dose interruptions as provided by the investigator on the eCRF study drug administration page for data collected between the time of start of combination treatment and discontinuation/completion of combination treatment.

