During Screening, patients on a stable dose of pirfenidone may return for the Baseline Visit (Study Day 1) as soon eligibility has been confirmed. At this visit, they will have nintedanib added to the ongoing pirfenidone treatment. Nintedanib dosing will start at 100 mg once daily (QD) and be titrated to 150 mg BID over 15 days, as tolerated, according to the schedule provided in protocol **Error! Reference source not found.**

The Sponsor will supply pirfenidone and nintedanib for use in the study; nintedanib will be supplied in 100 mg and 150 mg capsules to facilitate temporary dose reduction if required for the management of AEs.

Combination treatment will continue through Week 24, with monitoring by office visits and telephone contacts. Blood samples will be obtained from all patients for analysis of clinical laboratory values.

Patients will be encouraged to remain on stable doses of pirfenidone (1602–2403 mg/d) and nintedanib (200–300 mg/d) throughout the combination-treatment period, unless dosing is modified to manage an AE. Patients will return to the clinic for a final Follow-up Visit 28–35 days after the completion of combination treatment.

If one or both study treatments are prematurely discontinued or interrupted for ≥ 28 consecutive days, nintedanib treatment will end as will the patient's participation in the study; whether commercial pirfenidone treatment continues will be left to the judgment of the Investigator. The patient will then return to the clinic as soon as possible (≤ 7 days after the decision to discontinue nintedanib) for an Early Discontinuation Visit.

[figure not shown]
In addition, 28–35 days after the decision to discontinue nintedanib, the patient will return for a final Follow-up Visit.

A patient diary will be used to record AEs, daily dosing adherence for both pirfenidone and nintedanib, and concomitant medication use from the screening visit to the final Follow-up Visit. Also, patients will receive a wallet card that provides important information relevant to study participation.

On completion of study participation, patients may be prescribed appropriate IPF treatment at the discretion of the treating physician.

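### The whole-period average dose that decides the primary outcome includes the planned nintedanib start below 200 mg/d, so a completer in range on every post-titration day can be scored off target

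*SAP*

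**What the plan says.** The primary outcome (SAP V2.0, Section 2.2.5) is the proportion of patients who complete 24 weeks with pirfenidone at 1602–2403 mg/d and nintedanib at 200–300 mg/d. Section 4.7.1 makes the dose part operational: "Average daily dose information as defined in Section 4.7.2 will be used to assess whether a patient completed 24 weeks on target dose".

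Section 4.7.2 defines the average. Its numerator: "The average daily dose will be calculated by summing up the number of capsules taken during the combination treatment period". Its denominator: "divided by the number of days on combination treatment including treatment interruptions, as defined above". The exposure window covers "treatments administered from combination treatment start date up to the" completion or discontinuation date on the eCRF. Section 4.2.5 sets the start as "Date of first administration of nintedanib and pirfenidone on or after the Baseline visit". Below 200 mg/d is a separate category for nintedanib, with no tolerance or rounding rule.

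Appendix 1 describes the planned start: "Nintedanib dosing will start at 100 mg once daily (QD) and be titrated to 150 mg BID over 15 days", subject to tolerance. It also says that patients are encouraged to stay within 200–300 mg/d, and that "nintedanib will be supplied in 100 mg and 150 mg capsules to facilitate temporary dose reduction if required for the management of AEs".

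Section 2.2.5 lists as a secondary outcome the patient days of combination treatment with both drugs in range, and the synopsis repeats it. For patient days, Section 4.7.2 offers only this: "The total number of patient days on treatment, including and excluding dose interruptions, and the total number of patient days with dose interruptions".

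**The concern.** The first planned nintedanib days are below the lower bound of the range and inside the averaging window. Nothing shown in the SAP sets them aside. For a patient who then takes 200 mg/d, dose and bound coincide, so no slack exists to absorb the low start. Such a patient can be in range on every day after titration and still fail the dose criterion.

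The measure at stake is the primary tolerability proportion. A spell at 200 mg/d is foreseeable, because the smaller capsule is supplied for dose reduction. The average-dose categories in Section 4.7.2 use the same whole-period average, so they would not separate this patient from one who was below range after titration.

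**Working it through.** **Inputs**
- Range 200–300 mg/d: Section 2.2.5.
- Treatment length 168 days, the Week 24 target day, with window 155 to 174: Table 5, Section 4.9.
- Start at 100 mg/d and titration over 15 days: Appendix 1. The day-by-day schedule is not shown, so the number of days at 100 mg/d (d) is an assumption, ranged from 1 to 15.
- 80 patients and 85% completion: Section 2.3.
- Assumed: full capsule intake, and capsules converted to mg.

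**1. The plan's own figure.** 0.85 ± 1.96 × √(0.85 × 0.15 / 80) = 0.85 ± 0.078, or 77.2% to 92.8%. This reproduces Section 2.3. The SAP gives no figure for the average dose itself.

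**2. Held at 200 mg/d after d days at 100.** Average = (100d + 200(168 − d)) / 168.

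| d | Average, mg/d |
|---|---|
| 1 | 199.4 |
| 7 | 195.8 |
| 14 | 191.7 |
| 15 | 191.1 |

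Over treatment lengths of 155 to 174 days the range is 190.3 to 199.4. One day at 100 mg/d is enough, so the result does not depend on the unseen schedule.

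**3. With k days at 300 mg/d.** Average = 200 + 100(k − d)/168. The patient is off target whenever k < d. For d = 7, k = 6 gives 199.4 and k = 7 gives 200.0.

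**4. At 300 mg/d after titration.** With 15 days at 100: (1500 + 153 × 300)/168 = 282.1. With 1 day at 100 and 14 at 200: (100 + 2800 + 153 × 300)/168 = 290.5. Both are well inside the range.

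**5. From the end of titration.** The patient in step 2 averages exactly 200.0, and the patient in step 3 at least 200.0. With one missed 100 mg capsule in 153 days, the step 2 patient averages (200 × 153 − 100)/153 = 199.35 and still fails.

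**6. Direction.** The whole-period average is a day-weighted mean of the titration and post-titration averages. If the titration average is at most 200 and the whole-period average is at least 200, the post-titration average is at least 200. Under that condition, counting titration days can only lower the proportion.

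**7. Size per patient.** 1/80 = 1.25 points, against a planned half-width of 7.8 points at 85%. The number of such patients cannot be derived. Purely as an illustration, 1, 3 or 6 patients would be 1.25, 3.75 or 7.5 points.

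**8. Why days in range add information.** The averages are taken per drug and include interruption days, so higher doses can offset days off drug. Suppose each drug has one 27-day gap after titration, not overlapping, with otherwise 2403 and 300 mg/d. Pirfenidone averages 2403 × 141/168 = 2016.8 mg/d. Nintedanib averages 233.9 to 242.3 mg/d, which is the step 4 total less 27 × 300, over 168. Both pass, yet both drugs are in range on only (153 − 54)/153 = 64.7% of post-titration days. The outcome can be read as an average, so this limits interpretation and is not an error.

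**The case against.** The strongest reply is about cause. The plan goes on from 100 mg to 150 mg twice daily as tolerated, and a patient who completes that course passes easily. The failing patient did not reach 300 mg/d or spent fewer days there than at 100, plausibly because of a tolerability problem, which is what the outcome measures. This stands. A reader might infer that patients fail for titration alone or for following the plan. The documents do not support that, because the failure needs both the low start and the shortfall from 300 mg/d.

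A second reply is that a post-titration average leaves the tight bound in place (step 5) and drops early interruptions and missed doses. The outcome speaks of 24 weeks, so the whole-period average is a defensible choice. This also stands, and it argues against simply replacing the primary average.

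Third, such patients can be identified from other planned outputs: last dose administered, dose modifications with reasons, and the listings of eCRF and derived data. Completion regardless of dose is reported with its interval. This reduces the harm, but the primary proportion itself would still mix the two kinds of patient.

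A reader might also infer from the capsule wording that the average is not in mg. Section 4.7.2 gives total dose in mg and categories in mg/d, so the conversion is implied. It is a detail to write down.

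**Conclusion.** The point holds for a defined group: completers with full intake, at 200 mg/d after the planned start, with fewer days at 300 than at 100 mg/d. They average below 200 mg/d (199.4 to 191.1 over 168 days for 1 to 15 days at 100 mg and none at 300). They are scored off target although every post-titration day is in range. Each such patient lowers the primary proportion by 1.25 points if 80 are analyzed.

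The documents do not support a claim that the primary result is materially biased. The number affected is unknown. The offsetting in step 8 works the other way, so the net direction is unknown too. The study is descriptive, with no test or threshold. The conclusion rests on full intake and on conversion of capsules to mg, and not on the titration schedule.

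**What to change.** Before database lock:

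1. Reconcile Sections 2.2.5, 4.7.1 and 4.7.2 with the titration described in Appendix 1, and state how planned titration days count toward the dose criterion.
2. Beside the whole-period result, present the on-target proportion with its 95% CI using the nintedanib average in mg (capsules times strength) from the end of the planned titration period. Use the same cut for every patient, not each patient's own titration. State in advance which version is primary.
3. Tabulate patient days with both drugs in range, as the secondary outcome requires, if the drug log supports it. The diary records daily adherence, but the SAP does not show whether day-level doses reach the log. If they do not, only steps 1 and 2 apply.

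The cost is minor wording and programming. The report must state that the post-titration average covers about 153–154 days, leaves out early interruptions and missed doses, and remains sensitive at exactly 200 mg/d. No dosing or clinical rule changes.

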2.2.5 Safety Outcome Measures

The primary safety outcome measure is:

- Proportion of patients who complete 24 weeks of combination treatment on pirfenidone at a dose of 1602–2403 mg/d and nintedanib at a dose of 200–300 mg/d.

Secondary safety outcome measures are:

- Proportion of patients who discontinue pirfenidone, nintedanib, or both study treatments because of adverse events before the Week 24 visit,
- Total number of patient days of combination treatment with pirfenidone at a dose of 1602–2403 mg/d and nintedanib at a dose of 200–300 mg/d,
- Total number of days from the initiation of combination treatment to discontinuation of pirfenidone, nintedanib, or both study treatments,
- Frequency and timing of Adverse Events (AEs) and Serious Adverse Events (SAEs).

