- hepatic side effects (MedDRA AEGT: Esbriet - Potential Hy's Law AEGT' see [Appendix 4](#)),
 - all and related clinical significant vascular event (as angina pectoris, myocardial infarction, transient ischaemic attack (TIA), stroke) (Defined as any AE included in the MedDRA SMQs Ischemic heart disease, Central nervous system vascular disorders, Haemorrhages, Embolic and thrombotic events),
 - all and related ischemic heart disease (MedDRA SMQ: Ischemic heart disease)
 - all and related cerebrovascular event (MedDRA SMQ: Central nervous system vascular disorders),
 - all and related bleeding event (MedDRA SMQ: Haemorrhages),
 - all and related thromboembolic event (MedDRA SMQ: Embolic and thrombotic events),
 - all and related major adverse cardiac event (MACE), (Specific terms from SMQs Arrhythmia related investigations, Signs and symptoms, Cardiac arrhythmia terms (incl bradyarrhythmias and tachyarrhythmias), Cardiac arrhythmias, Cardiac failure: Cardiac arrest, Cardiac death, Cardio-respiratory arrest, Sudden cardiac death, Sudden death, Ventricular asystole, Agonal rhythm, Sinus arrest, Pulseless electrical activity, Torsade de pointes, Ventricular fibrillation, Ventricular flutter, Ventricular tachycardia, Cardiac fibrillation, Cardiac flutter.)
 - all and related photosensitivity or rash (MedDRA Preferred terms Nodular rash, Photodermatosis, Photosensitivity reaction, Pruritus, Pruritus generalized, Rash, Rash erythematous, Rash generalized, Rash macular, Rash maculo-papular, Rash popular, Rash pruritic, Solar dermatitis, Solar urticarial, Sunburn, Erythema, Dry skin),
 - all and related gastrointestinal (GI) perforation (MedDRA SMQ: Gastrointestinal perforation, ulceration, haemorrhage or obstruction: sub-category Gastrointestinal perforation),
 - all and related TEAEs leading to death,
 - all and related TEAEs leading to treatment discontinuation,
 - all and related TEAE resulting in hospitalization or prolonged hospitalization.
- . For related TEAEs the relationship to pirfenidone, nintedanib or both investigational drugs will be assessed.

The number and percentage of patients with CTCAE grade 3-4 laboratory liver test results will also be included in this overview.

If relationship to study drug is missing, the event will be presented in the 'All TEAEs' column. A listing presenting all AEs with missing relationship will be added.

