The following categories of TEAEs as presented in the overview will be summarized by system organ class (SOC) and preferred term (PT):

- all and related treatment-emergent adverse events (TEAE),
- all serious treatment-emergent adverse events (serious TEAE),
- all non-serious treatment-emergent adverse events (non-serious TEAE),
- all severe (Grade 3 – 5) treatment-emergent adverse events (severe TEAE),
- all TEAEs resulting in hospitalization or prolonged hospitalization

Similar summary presentations will be provided for patients with TEAEs leading to dose modification.

Frequencies and percentages of patients experiencing (at least) one event in the respective category will be presented by decreasing frequencies. If patients have more than one AE within a SOC or PT they will be counted only once for the respective SOC or PT. Total numbers of TEAEs will be provided for each SOC and overall.

Special interest in this study will be on assessment of treatment discontinuation. Therefore, TEAEs leading to treatment discontinuation will be summarized for TEAEs leading to discontinuation of any drug, and for TEAEs leading to discontinuation of both treatments, to pirfenidone alone or to nintedanib alone. Additional presentations for the following categories of TEAEs leading to treatment discontinuation will be presented:

- Serious TEAEs).
- GI event,
- Photosensitivity reaction or rash
- TEAEs by intensity.

All TEAEs indicating "Action taken with pirfenidone/nintedanib due to SAE/AE" = "Drug withdrawn" in the eCRF will be included in these summaries.

Numbers and frequencies of patients with TEAEs by most extreme CTCAE Grade will be provided for any TEAEs and for each SOC and PT. In case the most extreme intensity is missing, it will be replaced by the initial intensity. If both most extreme and initial intensity are missing, AE will be included in the summaries for grade 3 to 5 AEs (i.e. in the total column) and a column for "missing" will be added.

The timing of TEAEs will be assessed by presenting numbers of patients with TEAEs occurring in the first 28 days (Days 0 – 28), from Day 29 to Day 84 (Weeks >4 - 12), and for the total study period by SOC and PT.

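### The only AE-discontinuation proportion with a 95% CI counts the main reason alone; the by-drug count closer to the stated secondary outcome has no CI and a longer window

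*SAP*

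**What the plan says.** All references are to SAP Version 2.0.

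- **Outcome.** Section 2.2.5 lists this secondary safety outcome: "Proportion of patients who discontinue pirfenidone, nintedanib, or both study treatments because of adverse events before the Week 24 visit". It does not require the event to be the main reason.
- **Estimate with an interval.** Section 4.7.1 states: "The number and percentage of patients who discontinued combination treatment because of an adverse event (with 95% CI) will also be presented". The next sentence limits the count to patients who reported 'Adverse Event' "as the main reason for treatment discontinuation". The statistical methods in the synopsis (Appendix 1) promise the same proportion with a 95% CI, without that limit.
- **Second count.** The overview table in 4.7.3 gives the number and proportion of patients with "all and related TEAEs leading to treatment discontinuation". Further tables follow, with results "summarized for TEAEs leading to discontinuation of any drug, and for TEAEs leading to discontinuation of both treatments, to pirfenidone alone or to nintedanib alone". Such tables take every TEAE whose recorded action is 'Drug withdrawn', whatever main reason the discontinuation form gives. No CI is mentioned.
- **Window of the second count.** Sections 4.2.3 and 4.7.3 define TEAEs through 28 days after completion or early discontinuation of combination treatment.
- **Consequence of stopping one drug.** Under the synopsis, if one or both drugs are stopped early or interrupted for at least 28 consecutive days, "nintedanib treatment will end as will the patient's participation in the study".

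**The concern.** The outcome in 2.2.5 has three elements: a stop of either drug or both, attribution to an AE, and a stop before the Week 24 visit. The plan has two outputs that could serve as its estimate. They draw on different eCRF fields, and neither is named as the secondary outcome. The one with an interval decides attribution from a single main reason, which neither 2.2.5 nor the synopsis asks for. The one that looks at each drug has a wider time window and no interval.

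Tolerability is the primary objective, and 4.7 names early discontinuations among the endpoints of main interest. The sample-size text in 2.3 is built on AE-discontinuation rates, so readers will set this trial's figure beside those rates. If the two outputs differ, the choice of which to report as the secondary outcome is left until the data have been seen.

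**Working it through.** **Step 1. Outcome and outputs side by side**

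| Element | Outcome (2.2.5) | 4.7.1 proportion | 4.7.3 tables |
|---|---|---|---|
| What is stopped | Either drug or both | Combination treatment | Any drug, both, each alone |
| AE attribution | Because of AEs; no field named | One main reason | AE action 'Drug withdrawn' |
| Time limit | Before the Week 24 visit | Early stops of the combination | Events to 28 days after the combination ends |
| 95% CI | Promised in the synopsis | Yes | None stated |
| Split by drug | Drugs named separately | None | Yes |

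**Step 2. Is 'combination treatment' narrower than 'either drug'?** No. Under the synopsis rule, a premature stop of one drug ends nintedanib treatment and study participation. It is therefore also an early discontinuation of the combination. The narrowing in 4.7.1 comes only from the main-reason rule.

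**Step 3. Patients on whom the outputs can differ**

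- (a) 'Drug withdrawn' for an AE before Week 24, another main reason: in 4.7.3, not in 4.7.1.
- (b) Main reason 'Adverse Event', no 'Drug withdrawn' record: in 4.7.1, not in 4.7.3.
- (c) Completed 24 weeks, then pirfenidone withdrawn for an AE within the following 28 days: can enter 4.7.3, but is outside the outcome. The amendment rationale for 4.7.3 mentions study pirfenidone taken after completion, up to the Follow-up visit, so this case is possible.

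The documents give no count for (a), (b) or (c).

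**Step 4. The plan's own precision figure.** Section 2.3 gives 77.2% to 92.8% for 68 of 80 completers. With p ± 1.96 × √(p(1 − p)/n):

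0.85 ± 1.96 × √(0.85 × 0.15/80) = 0.85 ± 1.96 × 0.0399 = 0.85 ± 0.078, which is 77.2% to 92.8%.

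The figure reproduces. The plan gives no corresponding figure for AE discontinuation and names no interval method in 4.7.1, so both Wald and exact (Clopper-Pearson) limits follow.

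**Step 5. Size per patient.** At n = 80, each patient of type (a) is worth 1/80 = 1.25 percentage points. Starting counts and numbers missed are assumptions. Eight of 80 (10.0%) is close to the 24-week nintedanib rate of 10%-11% assumed in 2.3. Twelve of 80 (15.0%) is the complement of the assumed 85% completion.

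| Main reason AE | Added as type (a) | Total | Proportion | Wald 95% CI | Exact 95% CI |
|---|---|---|---|---|---|
| 8 | 0 | 8 | 10.0% | 3.4-16.6 | 4.4-18.8 |
| 8 | 1 | 9 | 11.25% | 4.3-18.2 | 5.3-20.3 |
| 8 | 2 | 10 | 12.5% | 5.3-19.7 | 6.2-21.8 |
| 8 | 4 | 12 | 15.0% | 7.2-22.8 | 8.0-24.7 |
| 12 | 0 | 12 | 15.0% | 7.2-22.8 | 8.0-24.7 |
| 12 | 4 | 16 | 20.0% | 11.2-28.8 | 11.9-30.4 |

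With none of type (a) and none of type (b), the two fields give the same count of stops before Week 24.

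**The case against.** The strongest reply is that the plan already reports what matters. Section 4.7.3 tabulates AE-driven withdrawals of any drug, both, and each alone, regardless of main reason. Reasons for early discontinuation are tabulated in 4.4.1, and details are listed. Section 4.7.1 delivers the proportion with CI that the synopsis promised, and the main reason on the discontinuation form is a fair reading of 'because of'. Because it concerns early stops, it also fits the Week 24 limit reasonably well. Everything is descriptive, and no stated decision depends on this proportion.

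Most of this stands. The count is not absent, and the main-reason rule is a defensible disposition summary. The 28-day window is also a limited problem: nintedanib ends with the combination, so mainly pirfenidone taken after completion could add cases. What the reply leaves open is which count is the secondary outcome, and why the count that uses all AE-driven withdrawals has no interval and a different window.

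Three stronger readings are tempting, and the documents support none of them:

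- A reader might infer that the 4.7.1 figure is biased low. It can miss patients, but no shortfall is shown, and it is zero if the fields agree.
- A reader might infer that AE-driven stops are commonly filed under another reason. Nothing in the SAP says so.
- A reader might infer that single-drug stops escape 4.7.1 because it refers to combination treatment. Step 2 shows otherwise.

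**Conclusion.** The point holds as a mismatch between outcome and analysis. The only AE-discontinuation proportion with a 95% CI applies a main-reason limit that the outcome does not contain, and so can leave out patients whose drug was withdrawn for an AE. The by-drug count that includes them lacks an interval, runs past the outcome's time limit and is not tied to the outcome.

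The effect is 1.25 percentage points per missed patient at n = 80. The number missed cannot be known from the documents and may be zero. The rows in the working that add patients are assumptions about scale, not estimates. The primary outcome, sample size and error rates are untouched. This is a cheap improvement worth making before database lock; it does not show that the reported figure would be wrong.

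**What to change.** Change 4.7.1 as follows.

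- **Define the secondary outcome there.** Count patients in the Safety Population with any TEAE whose action is 'Drug withdrawn' for pirfenidone or nintedanib, where the stop falls before the Week 24 visit. The discontinuation date already defined in 4.2.5 can supply the timing.
- **Report it** for any drug, both drugs, pirfenidone alone and nintedanib alone, each with a 95% CI and a named interval method.
- **Keep the main-reason count** as a supporting disposition row.
- **List every patient for whom the two fields disagree**, in both directions, including any with main reason 'Adverse Event' but no 'Drug withdrawn' record. The by-drug split may not be available for those patients, so they should be visible rather than silently dropped.
- **Add a sentence in 4.7.3** saying that its tables use the full TEAE window and may therefore differ from the outcome in 4.7.1.

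The cost is one derived flag, a short listing and a few lines of text, all from eCRF fields the SAP already uses. The reported proportion may become slightly less favourable. If type (b) patients occur, they pull it the other way, which is why the listing is needed.
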